### 11.3 Evaluating Adverse Events

The Investigator will determine the seriousness, intensity, and causality of an AE associated with the use of the study drug (i.e., events where there is a reasonable possibility that the event may have been caused by the study drug) based on the definitions that follow.

#### 11.3.1 Serious Adverse Events

*(Notify Medpace Safety within 24 hours; document on eCRF)*

The SAE definition and reporting requirements are in accordance with Title 21 Part Code of Federal Regulations (CFR) 312.32 and the Guidance for Industry and Investigators Safety Reporting Requirements for Investigational New Drug (INDs) and Bioavailability /Bioequivalence Studies.

SAE: An AE is considered "serious" if, in the view of either the Investigator or sponsor, it results in any of the following outcomes:

- **Death:** This includes any death that occurs while the subject is “on study” through the last study visit.
  - Note:** Death is an outcome of an AE, and not an AE. The event(s) that caused death (e.g., illness, accident) is the SAE. Death due to any other cause(s) must also be reported as an outcome of the reportable SAE.
- **Life-threatening adverse drug event:** An AE or suspected adverse reaction is considered “life threatening” if, in the view of either the Investigator or sponsor, its occurrence places the patient or subject at immediate risk of death. It does not include an AE or suspected adverse reaction that, had it occurred in a more severe form, might have caused death.
- **Inpatient hospitalization or prolongation of existing hospitalization:**

In the absence of an AE, the Investigator should not report hospitalization or prolongation of hospitalization. This is the case in the following situations:

  - Hospitalization or prolongation of hospitalization is needed for a procedure required by the protocol
  - Hospitalization or prolongation of hospitalization is part of routine procedure followed by study center

- Hospitalization for survey visits or annual physicals
- Hospitalization for observation with release within 24 hours

In addition, a hospitalization planned before the start of the study for a pre-existing condition, which has not worsened, does not count as an SAE.

- **Persistent or significant incapacity or substantial disruption of the ability to conduct normal life functions**
- **Congenital anomaly/birth defect**
- **Important medical event:** An event that may not result in death, be life threatening, or require hospitalization may be considered an SAE when, based upon appropriate medical judgment, it may jeopardize the subject and may require medical or surgical intervention to prevent one of the outcomes listed in this definition.

### 11.3.2 Overdose

An overdose is defined as a significant variation from the recommended/scheduled dosage for a product. The dosing for this study will be conducted in a controlled clinical setting and an overdose is not anticipated. However, in the event of an accident, for this study, an overdose of SYNT001 is considered a dose that is two-fold higher than the intended dose for the subject.

### 11.3.3 Non-Serious Adverse Events

*(Document on eCRF)*

All other AEs, not fulfilling the previous definitions, are classified as non-serious.

### 11.3.4 Protocol-Related Adverse Events

AEs that are not test drug related may nevertheless be considered by the Investigator or the Medical Monitor to be related to the conduct of the clinical study. That is, the event may be related to the fact that a subject is participating in the study. For example, a protocol-related AE may be an event that occurs during a screening period or that is related to a procedure required by the protocol.

### 11.3.5 Assessment of Causality

A medically qualified Investigator must assess the relationship of any AE (including SAEs) to the use of the investigational product, as related or not related, based on clinical judgment and using all available information, and may include consideration of the following factors:

- Possible alternative causes of the AE, including the disease under treatment, pre-existing conditions, concomitant use of other drugs, and presence of environmental or genetic factors.
- The temporal association between drug exposure and onset of the AE.
- Whether the manifestations of the AE are consistent with known actions or toxicity of the investigational product.
- The AE resolved or improved with decreasing the dose or stopping use of the investigational product (dechallenge). Judgment should be used if multiple products are discontinued at the same time.

The causal relationship between the study medication and the AE will be assessed using one of the following categories:

**Not Related:** Factors consistent with an assessment of Not Related include:

- Temporal relationship is lacking (e.g., the event did not occur within a reasonable time frame following administration of the study medication); or
- Other causative factors more likely explain the event (e.g., a pre-existing condition, other concomitant treatments).

**Related:** Factors consistent with an assessment of Related include:

- There is a positive temporal relationship (e.g., the event occurred within a reasonable time frame following administration of study medication); or
- The AE is more likely explained by the investigational product than by another cause (i.e., the AE shows a pattern consistent with previous knowledge of the investigational product or the class of the investigational product)

### 11.3.6 Recording Adverse Events

All AEs (including SAEs) are to be accurately recorded on the Adverse Event page of the subject's eCRF. The severity of each AE will be graded using the NCI CTCAE, Version 4.03. The date of onset as well as the end date of the event also should be recorded or the event should be entered as "ongoing". In addition, the method used to treat the AE and the outcome of the AE also will be noted. The Investigator will assess the relationship of the event to study drug.

### 11.3.7 Planned Hospitalization

A hospitalization planned by the subject prior to the first dose of study medication is considered a therapeutic intervention and not the result of a new SAE and should be recorded as medical

history. If the planned hospitalization or procedure is executed as planned, the record in the subject's medical history is considered complete. However, if the event/condition worsens during the trial, it must be reported as an AE.

### **11.3.8 Reporting Pregnancies**

If a female subject or the female partner of a male subject becomes pregnant during the course of the study, the Investigator must report the pregnancy to the Medpace Safety using the **Pregnancy Reporting Form** within **24 hours** of becoming aware of the event. The Investigator must obtain consent to collect pregnancy information (including the status of the newborn, if applicable).

If some of the information required for completion of the Pregnancy Reporting Form is unavailable at the time of the initial report, follow-up reports will be completed and submitted within 24 hours of becoming aware of the new information. Any pregnancy will be followed through delivery for the observation of any SAEs. Any SAE that occurs during pregnancy must be recorded on the SAE report form in the EDC system (e.g., maternal serious complications, therapeutic or spontaneous abortion, ectopic pregnancy, stillbirth, neonatal death, congenital abnormality, birth defect) and reported within 24 hours in accordance with the procedure for reporting SAEs (See Section 11.3.9).

### **11.3.9 Serious Adverse Event Reporting**

#### **11.3.9.1 Governing Regulatory Requirements**

Compliance with this request for prompt reporting is essential in that the sponsor is responsible for informing the US Food and Drug Administration (FDA) and other regulatory authorities as well as all other participating Investigators of the event.

Under FDA ruling (US Code of Federal Regulations, Title 21 CFR Part 312.32) and the ICH Guidelines for Clinical Safety Data Management Definitions and Standards for Expedited Reporting, the sponsor is required to submit written documentation, in the form of a safety report, detailing:

- Any event associated with the use of the drug, that is both serious and unexpected, or
- Any finding from tests in laboratory animals that suggests a significant risk for human subjects, including reports of mutagenicity, teratogenicity, or carcinogenicity.

Written submission must be made by the sponsor to the FDA as soon as possible and in no event later than 15 calendar days after the sponsor's initial notification of the event. The sponsor shall also inform all Investigators.

**11.3.9.2 Time Frame for Reporting**

Any death, SAE or pregnancy experienced by the subject after informed consent through the last study visit, regardless of relationship to study drug, , must be promptly reported (within 24 hours of the Investigator becoming aware of the event) by telephone or electronic transmission to the sponsor (or designee).

Contact information for **SAE** reporting:

Medpace Clinical Safety  
Medpace SAE hotline:  
Telephone: PPD [redacted] dial P or PPD [redacted] dial P  
Facsimile: PPD [redacted] or PPD [redacted] D  
e-mail: PPD [redacted]

Additionally, the Investigator will be able to contact the **Medical Monitor**:

### 11.3.9.3 Information to be Provided by the Investigator

SAEs must be recorded on the SAE form in the EDC system. This requirement includes all SAEs that occur after informed consent through the last study visit.

The minimum information required for SAE reporting includes identity of Investigator, site number, subject number, an event description, SAE term(s), onset date, the reason why the event is serious (i.e., the seriousness criteria) and the Investigator's assessment of the relationship of the event to study treatment. Additional SAE information including medications or other therapeutic measures used to treat the event, action taken with the study treatment due to the event, and the outcome/resolution of the event will be recorded. Paper forms for reporting SAEs will be provided to the study sites as back-up in case the EDC system is not accessible.

In all cases, the Investigator should continue to monitor the clinical situation and report all material facts relating to the progression or outcome of the SAE. Furthermore, the Investigator may be required to provide supplementary information as requested by Syntimmune or designee.

When reporting an SAE, the following additional points should be noted:

- When the diagnosis of an SAE is known or suspected, the Investigator should report the diagnosis or syndrome as the primary SAE term, rather than as signs or symptoms. Signs and symptoms may then be described in the event description. For example, dyspnea should not be used as an SAE term if the diagnosis, which caused the dyspnea, is known to be malignant pleural effusion.
- Death should not be reported as an SAE, but as an outcome of a specific SAE, unless the event preceding the death is unknown. In the exceptional case where the events leading to death are unknown, then death may be used as an event term. If an autopsy was performed, the autopsy report should be provided.
- While most hospitalizations necessitate reporting of an SAE, some hospitalizations do not require SAE reporting, as follows:
  - Elective or previously scheduled surgery, e.g., a previously scheduled ventral hernia repair
  - Procedures for pre-existing conditions that have not worsened after initiation of treatment
  - Pre-specified study hospitalizations for observation
  - Events that result in hospital stays of less than 24 hours and that do not require admission, e.g., an emergency room visit for hematuria that results in a diagnosis of cystitis and discharge to home on oral antibiotics
- SAEs must, however, be reported for any surgical or procedural complication resulting in prolongation of the hospitalization.

#### **11.3.10 Regulatory Reporting**

Syntimmune (or designee) will process and evaluate all SAEs as soon as the reports are received. For each SAE received, Syntimmune will decide as to whether the criteria for expedited reporting have been met.

Syntimmune (or designee) will submit SAEs that meet the criteria for expedited reporting to the regulatory authorities in accordance with local regulations governing safety reporting. Reporting of SAEs by the Investigator to his or her IRB will be done in accordance with the standard operating procedures and policies of the IRB. Adequate documentation must be maintained showing that the IRB was properly notified.

### **11.3.11 Follow-up Information on a Serious Adverse Event (SAE)**

Appropriate diagnostic tests should be performed and therapeutic measures, if indicated, should be instituted. Appropriate consultation and follow-up evaluations should be carried out until the event has returned to baseline or is otherwise explained by the Investigator.

If all required information on the SAE form is not available at the time of the initial report, follow-up information will be completed in the EDC system.

## **11.4 Other Safety Considerations**

### **11.4.1 Laboratory Data**

All laboratory data obtained during the study should be reviewed. Any abnormal value that leads to a change in subject management (e.g., requirement for additional medication or monitoring) or is of clinical significance by the Investigator should be reported as an AE and/or SAE as appropriate, unless this value is consistent with values obtained before entry into the study.

### **11.4.2 Medication Errors**

Any medication error that results in an AE, even if it does not meet the definition of serious, requires reporting within 24 hours to the safety Medical Monitor.

### **11.4.3 Follow-Up of Adverse Events**

Any SAE or AE assessed as related to study drug must be followed until either resolution of the event or determination by the Investigator that the event has become stable or irreversible. The Investigator will follow all drug related AEs until there is a return to the subject's baseline condition, or until a clinically satisfactory resolution has been achieved. The appropriate follow-up visits must be scheduled and the specific tests repeated or performed as necessary. The status of all AEs will be documented as of the last study visit.

Where a diagnosis is possible, it is preferable to report this diagnosis rather than a series of terms (signs/symptoms) relating to the diagnosis.

## **11.5 Safety Monitoring for Dose Escalation**

Following dosing in each cohort, all safety/tolerability data (e.g., PEs, vital signs [including pulse oximetry], clinical safety laboratory tests, ECGs and AE/SAE assessments) as well as any available and relevant PD data collected through Day 42 will be reviewed by the DEC. A decision to escalate to the next cohort will be made. The recommendation may be to continue to

the next scheduled dose level, discontinue the study or to modify dosing to a dose less than the current dose or higher than the current dose but lower than the next planned dose.

## 12 STATISTICAL CONSIDERATIONS

All descriptive and inferential statistical analyses will be performed using the most recently released and available Statistical Analysis System (SAS) software, unless otherwise noted. Missing data will not be imputed unless otherwise stated. All clinical data captured will be provided in data listings. A Statistical Analysis Plan (SAP) and a Pharmacokinetic Analysis Plan (PAP) will be finalized prior to database lock.

### 12.1 General Design

All data for enrolled subjects will be presented in data listings by subject number.

Continuous data will be described using descriptive statistics: number of observations (n), mean, standard deviation (SD), median, minimum, and maximum. Frequencies and percentages will be used for summarizing discrete (categorical) data. When categorical data are presented, the percent will be suppressed when the count is zero to draw attention to the non-zero counts. The denominator for all percentages, unless otherwise specified, will be the number of subjects in the specified analysis population.

### 12.2 Sample Size Justification

Formal sample size calculations were not performed. The number of subjects was chosen based on feasibility and was considered sufficient to meet the study objectives.

### 12.3 Statistical Considerations

Detailed methodology for summary and statistical analyses of the data collected in this study will be documented in a statistical analysis plan (SAP). The SAP may modify the plans outlined in the protocol; any deviations from the previously described statistical plan will be described and justified in an SAP amendment. Additional statistical analyses other than those described in this section may be performed if deemed appropriate and will be described in the SAP. Methods of handling of missing data for different endpoints will be further specified in the SAP. In general, where individual data points are missing because of insufficient samples, dropouts, or other reasons, the data will be analyzed based on reduced denominators unless specified otherwise in the SAP.

Results will be summarized by cohorts.

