Methodology	
Two cohorts of 8 eligible subjects each will receive 5 once-weekly 60-minute infusions of SYNT001 in planned doses of 10 mg/kg or 30 mg/kg. Based on review of safety, PD, and clinical outcomes of these 2 cohorts, a third cohort of up to 8 subjects may be treated at another dose, with a maximum dose of 45 mg/kg, but may also be lower than 10 mg/kg or between 10 and 30 mg/kg, inclusive.
 
  
 Cohort	No. of subjects	Dose	
   
 1	8	SYNT001 10 mg/kg	
 
 2	8	SYNT001 30 mg/kg	
  
 
Cohorts will be dosed sequentially beginning with Cohort 1. The first 2 subjects will be dosed at least 24 hours apart. A review of the 24-hour safety data for the first subject will be performed to ensure that there are no overt safety concerns before dosing the second subject. A review of the 7-day safety data for the first 2 subjects will be performed prior to dosing the remaining 6 subjects in the cohort. This evaluation will include a review of AE/SAE reports, vital sign assessments, physical examinations, ECGs, and clinical laboratory testing. The seriousness, severity, and relatedness of AEs/SAEs will also be considered in the safety evaluation. Safety data will be reviewed on a continuous basis throughout the study. All safety data and any available and relevant PD data through Day 42 (2 weeks after the last subject's last dose in Cohort 1) will be reviewed by a dose escalation committee before Cohort 2 is initiated. Escalation to Cohort 2 will proceed if there are no concerning safety signals and the review of available and relevant PD data supports advancing to a higher dose. The dose for Cohort 2 will be finalized after review of the safety and PD data, but will not exceed 30 mg/kg. Cohort 2 and Cohort 3, if added, will be dosed per the same schedule as Cohort 1.
 
On days where study drug is administered, vital sign and pulse oximetry measurements will be collected immediately prior to the infusion; 15, 30, and 45 minutes after the start of the infusion; at completion of the infusion; and 30 minutes, 1 hour and 2 hours following completion of the infusion.
 
On Days 0 and 28, PK blood samples will be collected prior to infusion start and then over the subsequent 48 hours. Subjects will remain at the clinic through the
	Cohort	No. of subjects	Dose	1	8	SYNT001 10 mg/kg	2	8	SYNT001 30 mg/kg

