Dose-escalation rules	
Dose escalation decisions will be made by a Dose Escalation Committee (DEC) and will be based on safety and pharmacodynamic evaluations including but not limited to, dose-limiting toxicities, AEs, SAEs, and total IgG levels.
 
Dose-limiting toxicity (DLT) will be defined generally as severe (Grade 3) AEs occurring in <math>\geq 2</math> subjects that are determined to be clinically significant and considered related to study drug.
 
If 2 or more subjects at any time in any cohort (8 total subjects per cohort) have Grade 3 AEs that are determined to be clinically significant and considered to be related to study drug, dosing will be halted within that cohort and dose-escalation to a higher dose will not occur. If the dose-escalation stopping rule is met during Cohort 1 (10 mg/kg) all safety data and all available pharmacodynamics data will be reviewed and the cohort may resume (if applicable) or a new cohort may be added, at a dose at least 50% lower than the 10 mg/kg dose. If the stopping rule is not met in Cohort 1 (10 mg/kg), dose-escalation may proceed up to a maximum of 30 mg/kg. If the dose-escalation stopping rule is met for the first time during Cohort 2, all safety data and all available pharmacodynamics data will be reviewed and the cohort may resume (if applicable) or a new cohort may be added at a dose at least 30% lower than the Cohort 2 dose. If the stopping rule is not met in Cohort 2, dose-escalation may proceed up to a maximum of 45 mg/kg; however, this cohort may also receive a dose equal to or less than 30 mg/kg based on evaluation of all safety and pharmacodynamic data.

Study stopping rule	
If any subject experiences a life-threatening AE (Grade 4) that is considered to be related to study drug, any further dosing in all enrolled subjects will be suspended until the DEC has evaluated the event and determined the next appropriate course of action. At any time during the study, the study may be discontinued if the DEC determines that further drug exposure would pose an undue risk to subjects.

Individual stopping rule	
Dosing for any individual subject will be discontinued (i.e., further treatment with the study drug will not be given) if the subject experiences any study drug-

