### 3 STUDY OBJECTIVES

#### 3.1 Primary Objective

The primary objective of this study is to evaluate the safety and tolerability of 5 once-weekly IV infusions of SYNT001 at different dose levels in subjects with chronic pemphigus (vulgaris or foliaceus).

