## **8.4 Stopping Rule**

### **8.4.1 Dose-Escalation Stopping Rule**

Dose escalation decisions will be made by a Dose Escalation Committee (DEC) and will be based on safety and pharmacodynamic evaluations including but not limited to, dose-limiting toxicities, AEs, SAEs, and total IgG levels.

Dose-limiting toxicity (DLT) will be defined generally as severe (Grade 3) AEs occurring in  $\geq 2$  subjects that are determined to be clinically significant and considered related to study drug.

If 2 or more subjects at any time in any cohort (8 total subjects per cohort) have Grade 3 AEs that are determined to be clinically significant and considered to be related to study drug, dosing will be halted within that cohort and dose-escalation to a higher dose will not occur. If the dose-escalation stopping rule is met during Cohort 1 (10 mg/kg) all safety data and all available pharmacodynamics will be reviewed and the cohort may resume (if applicable) or a new cohort may be added at a dose at least 50% lower than the 10 mg/kg dose. If the stopping rule is not met in Cohort 1, dose-escalation may proceed up to a maximum of 30 mg/kg. If the dose-escalation stopping rule is met for the first time during Cohort 2, all safety data and all available pharmacodynamics will be reviewed and the cohort may resume (if applicable) or a new cohort may be added at a dose a minimum of 30% lower than the Cohort 2 dose. If the stopping rule is not met in Cohort 2, dose-escalation may proceed up to a maximum of 45 mg/kg; however, this cohort may also receive a dose equal to or less than 30 mg/kg based on evaluation of all safety and pharmacodynamic data.

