## **12.5 Safety Data**

Safety observations and measurements include AEs, safety laboratory tests, vital sign measurements, PEs, and ECGs.

Treatment-emergent AEs will be summarized using the Medical Dictionary for Regulatory Activities (MedDRA®; Version 19 or higher) System Organ Class (SOC) and preferred term, classified from verbatim terms. The incidence and percentage of subjects with at least 1 occurrence of a preferred term will be included, using the most severe grade. The number of events per preferred term will also be summarized. Causality (relationship to study treatment) will be summarized separately.

AEs, SAEs, and AEs leading to withdrawal, dose modification, or treatment discontinuation will be listed by subject, cohort, and overall per SOC and preferred terms. Duration of AEs will be determined and included in listings, along with action taken and outcome.

Laboratory results will be summarized by cohort. Incidence of laboratory abnormalities will be summarized. The worst on-study grade after the first dose of study drug will be summarized. Results for variables that are not coded will be presented in the listings as below, within, and above the normal limits of the local laboratory.

Vital sign measurements and change from baseline will be summarized at each scheduled time point by cohort using descriptive statistics.

Arithmetic mean of parameters from triplicate ECG will be calculated first for each participant at each planned time point. Then summary statistics of ECG test parameters (mean of triplicate) and change from baseline to each post-dose time point will be calculated. Shift tables for ECG test result category change (normal, abnormal, clinically abnormal) from pre-dose to each post-dose time point showing number and percentage of subjects with movement between categories will be presented by treatment group. Frequency and percentage of subjects experiencing potential QTc prolongation ( $QTcF > 450$ ) will be summarized at each time point by cohort.

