## **12.6 Pharmacodynamic/Activity Data**

PD results will be summarized by cohort.

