## **12.7 Immunogenicity Data**

Immunogenicity results will be summarized by cohort.

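### Objectives are set by dose level but most summaries are fixed by cohort, so if Cohort 3 repeats an earlier dose, subjects on the same dose are reported apart

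*Protocol*

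**What the plan says.** Section 3.1 sets the primary objective as the safety and tolerability of "5 once-weekly IV infusions of SYNT001 at different dose levels in subjects with chronic pemphigus". Section 3.2 uses the same unit, dose level, for PK, PD and disease activity.

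Section 12.3 then fixes the unit of reporting: "Results will be summarized by cohorts". Later subsections repeat it: "Laboratory results will be summarized by cohort" in 12.5 (where vital signs and QTcF are also by cohort), "PD results will be summarized by cohort" in 12.6 and "Immunogenicity results will be summarized by cohort" in 12.7. Section 12.4 on PK names no grouping, so the 12.3 rule applies by default. Within 12.5, ECG shift tables are by treatment group, a term the protocol does not define.

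On dosing, the synopsis allows an optional third cohort of up to 8 subjects, whose dose has a maximum of 45 mg/kg "but may also be lower than 10 mg/kg or between 10 and 30 mg/kg, inclusive". Sections 4.3, 6.8 and 9.1 say the same. Section 8.4.1 adds that, if the stopping rule is not met in Cohort 2, "this cohort may also receive a dose equal to or less than 30 mg/kg". If the stopping rule is met in Cohort 1, the synopsis says that "the cohort may resume (if applicable) or a new cohort may be added, at a dose at least 50% lower" than 10 mg/kg.

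**The concern.** A reporting unit should match the question asked. Here the question is about dose, and the unit is an enrolment group that need not correspond to one dose each. If Cohort 3 is given the dose of Cohort 1 or Cohort 2, the planned tables carry two rows for one dose and none for that dose as a whole. The study was sized on feasibility with no formal calculation, so the information per dose is already thin. Reporting it in halves gives up precision on exactly the quantity named in the primary objective.

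The protocol also never says how cohort, dose level and treatment group relate, so three terms are in play for what should be one or two groupings.

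**Working it through.** **The plan's own figure.** There is no power-based sample size to reproduce. The enrolment cap is stated as 27: 3 cohorts × 8 = 24, plus 3 × 1 replacement = 27. It reproduces.

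**Can Cohort 3 share a dose with an earlier cohort?** The planned doses are 10 mg/kg for Cohort 1 and 30 mg/kg for Cohort 2, with 30 mg/kg as the ceiling for Cohort 2. The permitted range for Cohort 3 runs from 10 to 30 mg/kg with both ends included, and Section 8.4.1 allows it to equal 30 mg/kg. So it may coincide with Cohort 1 or with Cohort 2.

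**What the split costs, as an illustration.** Take 8 subjects per cohort, a full Cohort 3 at a repeated dose, and ignore replacements: 8 + 8 = 16 on one dose.

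| Quantity | Formula | n = 8 | n = 16 |
|---|---|---|---|
| One-sided 95% upper bound, no events | 1 − 0.05^(1/n) | 31.2% | 17.1% |
| Exact two-sided 95% interval, 25% observed | Clopper-Pearson | 3.2–65.1% (2/8) | 7.3–52.4% (4/16) |
| Standard error of a mean, relative to n = 8 | √(8/n) | 1.00 | 0.71 |

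The standard error is therefore 1 − 0.71 = 29% smaller with 16. Cohort 3 may be smaller than 8. With 4 subjects (assumed), n = 12, the zero-event bound is 1 − 0.05^(1/12) = 22.1%, and the standard error is √(8/12) = 0.82 times that with 8, or 18% smaller.

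**The resumption wording.** These passages can only be set side by side.

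- Synopsis, Cohort 1 sentence: a comma precedes the dose reduction, so the reduction can be read as covering a resumed cohort as well as a new one.
- Synopsis, Cohort 2 sentence: no such comma.
- Section 8.4.1, both sentences: no such comma. The reduction reads most naturally with the new cohort only, and the dose of a resumed cohort is not stated.

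Section 12.3.2 accounts for differences between planned and received treatment, but only in the disposition, demographic and baseline displays.

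**The case against.** The strongest reply is that this is a contingency on a contingency. Cohort 3 may never be opened, and the protocol describes its dose as different from the others, which points away from a repeat. The study is descriptive, and Section 12 plans no confidence bounds or standard errors, so the figures above measure outputs that nobody has promised. Section 12.3 leaves detailed methodology to the SAP and lets it modify the plan, all data are listed by subject, and a reader can add two rows of 8.

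Much of that stands. It limits the size of the point and makes the numbers illustrative. It does not remove the point. The protocol is not silent but states a unit that does not match its objectives, and the inclusive range and Section 8.4.1 expressly permit a repeat. Counts can be added by hand, but medians cannot, and standard deviations only with extra work.

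Four stronger inferences are tempting and not supported:

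- *A cohort will mix doses.* This rests on one comma in one synopsis sentence that Section 8.4.1 lacks. No passage plainly says that a cohort resumes at another dose.
- *The adjustable Cohort 2 dose adds to the problem.* That dose is settled before Cohort 2 starts, so it neither mixes doses within the cohort nor, by itself, splits a dose between cohorts.
- *Every result is by cohort.* The ECG shift tables are not, and adverse event listings are by subject, cohort and overall.
- *Two same-dose groups would look like a dose effect.* Both would carry the same dose label, so they would not.

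**Conclusion.** The point holds in a limited form. Objectives are by dose level, most summaries are fixed by cohort, and the design lets Cohort 3 share a dose with Cohort 1 or Cohort 2. If it does, same-dose subjects are reported apart and the dose-level estimate is less precise than the data allow: a zero-event upper bound of 31.2% rather than 17.1%, and a standard error that pooling would cut by 29%. Those sizes assume a full Cohort 3 at a repeated dose and are smaller if it enrols fewer. If all cohorts receive different doses, nothing is lost. This is a worthwhile correction to a stated rule and does not threaten the study's conclusions.

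The differing wording on resumption is a separate matter of consistency. It bears on the summaries only if the reconciled text lets one cohort hold more than one assigned dose.

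**What to change.** In Section 12.3, replace the sentence with: *Results will be summarised by cohort and by dose level, pooling cohorts assigned the same dose.* Carry this into Sections 12.5 to 12.7, and use the same term in place of treatment group for the ECG shift tables. Keep the cohort summaries, because cohorts are dosed one after another and the stopping rule counts events per cohort.

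Separately, reconcile the synopsis dose-escalation rules with Section 8.4.1 on whether the dose reduction applies to a resumed cohort. If the reconciled text allows more than one assigned dose within a cohort, state that its summaries show those doses separately.

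The cost is a change of wording and one grouping variable. An extra table column appears only if a dose is repeated. It is best settled before the Cohort 3 dose is chosen, since the study is open-label and the earlier results will be known by then.
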